4.19.1 Allowed Medications

Subjects will be allowed to continue their regimen of analgesic medications from the time of the Screening Visit through and including the Day 120 visit. In this context, "analgesic medications" refers to medications prescribed and administered for the treatment of pain from diabetic neuropathy, and includes but is not limited to anticonvulsants, nonsteroidal anti-inflammatory agents, anti-depressants and muscle relaxants. As such, this includes medications taken on an "as needed" (prn) basis as well as those medications taken on a regular schedule. Medications identified as those taken for the subject's painful diabetic distal symmetric peripheral neuropathy will be auto populated in the subject's ePRO diary in order to capture the number of pills/capsules/tabs taken in the last 24 hours.

Medications prescribed for other indications are allowed and will be recorded as concomitant medications.

4.19.2 Prohibited Medications/Treatments

The following medications and therapeutics are prohibited throughout the study:

- Systemic steroids or topical steroids on the lower extremities
- Transcutaneous electrical neurostimulators (TENS units)
- Implanted neurostimulators
- Local injections
- Intrathecal infusion
- Acupuncture
- Surgery

5. WITHDRAWAL PROCEDURES

If a subject is withdrawn from study participation, the subject's enrollment in the study will terminate, study device application will be discontinued and no further data will be collected on the subject. Efforts will be made to perform all assessments scheduled for the Month 4 Visit (Day 121) prior to subject withdrawal in Part A, and Month 12 Visit (Day 361) prior to subject withdrawal in Part B.

A subject may be withdrawn from further study participation under the following circumstances:

- At the subject's request.
- Noncompliance with the protocol by the subject.
- Adverse Event (decision to be removed from study made by either the investigator or subject). The investigator must notify the sponsor immediately if a subject is withdrawn because of an AE.
- Decision by the investigator or sponsor that termination is in the subject's best medical interest or administrative decision for a reason other than that of an AE.
- Request for withdrawal by the subject for reasons other than an intolerable AE.
- Lost to follow-up, as determined by failure to respond to at least 2 telephone calls followed by certified letter sent to the subject's last known address. All attempts to contact the subject must be documented in the subject's source documents.

6. **RISK BENEFIT**

In a prior study evaluating PEMF therapy on pain sensitivity to different qualities of experimentally induced pain in subjects with 41 subjects with painful peripheral diabetic neuropathy, treatment with Provant was well tolerated. There were no adverse events were reported in that study for either treatment group. A review of the data with the use of Provant in multiple on-label and off-label uses supports the safety of Provant when used in its labeled twice-daily frequency of administration. The anticipated adverse events were mild to moderate with none being serious in nature. Moreover, non-thermal devices similar to Provant have been found to have a favorable risk-benefit profile in clinical trials. Accordingly, Regenesis Biomedical, Inc. has reviewed all reported adverse events in clinical studies and in post-market data collection and has concluded that the use of Provant as intended in this clinical trial does not present a potential for serious risk to the health of participants. In addition, preclinical data related to diabetic neuropathy and clinical data in different indications suggest that short and long-term benefits in subjects with painful peripheral diabetic neuropathy may occur. Therefore, the risk-benefit profile for participating in the current study appears to be favorable.

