7. STATISTICAL CONSIDERATIONS

The statistical analysis plan for this study will be described in detail in a separate Statistical Analysis Plan (SAP). The initial phase of this study is defined as *Part A* and represents the randomized double-blind portion of the study. Part B is the open-label extension phase where all subjects will receive active therapy.

The primary population for assessing efficacy and safety will be the *Intent to Treat (ITT) Analysis Set*, defined as all subjects who were enrolled into the study and issued a study device.

A secondary analysis of the individual efficacy endpoints will be conducted using the *Per Protocol* (*PP*) *Analysis Set*, defined as all subjects who were enrolled and completed \geq 70% use in treating with the study device.

Subjects will complete a 14-day run in period to obtain an average over the last 7 days in the runin period to obtain the NPRS score for qualification. Once the subject is determined to be eligible, the subject will be enrolled and randomized 1:1 to either an active or inactive sham device and become part of the *ITT and PP sets*.

Subjects in the *ITT and PP sets* will be instructed in the use of the devices for 120 days in the home environment. At months 1, 2, and 3 subjects will return to the clinic to complete PGI and review of adherence to treatment and diary entries. At month 3, subjects will return for completion of the WPAIQ, NeuroQoL and SPP measurements. Subjects will return to the clinic at day 121 for final evaluation and to complete the questionnaires, SPP, QST, and NCS.

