7.4 Sample Size

This is a Phase III study with a sample size of 170 patients (85 per treatment group). The sample size for the trial has been set at 170. Based on a previously conducted clinical trial assessing the efficacy and safety of the Provant Therapy System in a similar population, the mean \pm standard deviation change in the NPRS from baseline to 60 days was 1.79 ± 1.83 units. The data are derived from the open-label, single arm part of the trial in which all subjects received PEMF. Assuming a placebo effect of 40% results in an assumed between group difference of 1.07 units. Based on alpha = 0.05 and 90% power, a sample size of 62 patients per treatment group would be needed based on a two-sided sample t-test for the NPRS. A total sample size of 162 was estimated based on an assumed premature discontinuation rate of 30%.

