Moderate:	The event results in mild to moderate limitation in activity – some assistance may be needed; no or minimal medical intervention/therapy is required
Severe:	The event results in marked limitation in activity, assistance is usually required; medical intervention/therapy is required and hospitalization is possible

Each AE will also be independently judged by the investigator in terms of seriousness. A serious adverse event (SAE) is defined as any untoward medical occurrence that:

- Results in death, or
- Is life-threatening,

Note: The term "life-threatening" in the definition of "serious" refers to an event in which the subject was at risk of death at the time of the event; it does not refer to an event which hypothetically might have caused death if it were more severe.

- Requires inpatient hospitalization or prolongation of existing hospitalization,
- Results in permanent impairment of a body function or permanent damage to a body structure,
- Is a congenital anomaly/birth defect,

• Necessitates medical or surgical intervention to preclude any one of the outcomes listed in this definition.

All SAEs must be reported *immediately* (within 24 hours of knowledge of the event) by telephone and fax to the study manager:

[contact] Attention: Medical Monitor

The investigator will follow up with a written description of the SAE submitted to the sponsor within 3 days, including the results of the SAE investigation and any treatment(s) provided.

All adverse events will be followed until resolution or until the investigator assesses the subject's status has returned to normal.

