6. ANALYSIS POPULATIONS

The primary population for assessing efficacy and safety will be the Intent to Treat (ITT) Analysis Set, defined as all subjects who were enrolled into the study and issued a study device.

A secondary analysis of the individual efficacy endpoints will be conducted using the Per Protocol (PP) Analysis Set, defined as all subjects who were enrolled and their compliance for using the study device was $\geq 70\%$. For the specific tables of the individual efficacy endpoints generated based on the PP analysis dataset, an x will be added to the table number for differentiation.

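### Outcome collection ends at withdrawal with no off-device follow-up path, so at the assumed 30% discontinuation the ITT Month 4 pain score rests on earlier scores or imputation for at most 51 of 170 subjects

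*Protocol*

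**What the plan says.** Protocol 5 (Withdrawal Procedures) and SAP 4.4 carry the same rule. On withdrawal from study participation, "study device application will be discontinued and no further data will be collected on the subject". The listed grounds include "Noncompliance with the protocol by the subject", "Adverse Event (decision to be removed from study made by either the investigator or subject", a decision by the investigator or sponsor (medical or administrative), the subject's own request, and loss to follow-up.

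Three provisions soften the rule:
- The next sentence of Protocol 5 adds: "Efforts will be made to perform all assessments scheduled for the Month 4 Visit (Day 121) prior to subject withdrawal in Part A".
- NPRS diary entries made before withdrawal are kept.
- Protocol 11.1 states: "All adverse events will be followed until resolution".

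SAP 6 says: "The primary population for assessing efficacy and safety will be the Intent to Treat (ITT) Analysis Set". Protocol 7 gives the membership of that set as "defined as all subjects who were enrolled into the study and issued a study device". In Protocol 7.1 and SAP 11 the primary hypothesis concerns change in NPRS at 4 months.

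Protocol 7.4 sets the total sample size "based on an assumed premature discontinuation rate of 30" percent. For missing weekly scores, Protocol 7.1 plans multiple imputation with a pattern-mixture approach, plus an observed-data MMRM and a last-observation analysis. SAP 7.2 says missing values are not imputed and relies on the last recorded observation for the ITT comparison.

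**The concern.** An ITT comparison at Month 4 asks how the arms differ at that time among everyone issued a device. A subject removed for an adverse event, for poor adherence or by an investigator or sponsor decision has not necessarily declined to keep a pain diary. The rule nevertheless closes the diary, and no section describes a subject who is off the device but still reporting. Protocol 3.12.1 also ties the treatment-period score to the end of each morning session, so an off-device score has no defined time.

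An assessment brought forward to the day of withdrawal is not a Month 4 outcome. What remains is to carry an earlier score forward or to impute. Without post-withdrawal data, the assumption behind either choice cannot be checked in this trial. The size of the estimated benefit would then depend partly on that choice.

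**Working it through.** **Inputs.** Protocol 7.4 gives a difference of 1.07, SD 1.83, two-sided alpha 0.05, 90% power, 62 per group, 30% discontinuation and 170 planned (85 per arm). No split of the 30% by reason is given.

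**Reproducing the plan's figure.** n per group = 2 × (1.96 + 1.28)² × 1.83² / 1.07², which rounds up to 62, as stated. The total of 162 is 124 × 1.3 = 161.2, rounded up to two equal arms. The SAP states only that multiplier. Since 1 − 124/162 = 23.5% and 1 − 124/170 = 27.1%, neither total fully covers a 30% loss.

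**How many subjects.** 0.30 × 170 = 51 without a scheduled Month 4 value, and 119 (59.5 per arm) with one. This is a ceiling on what better follow-up could recover. If 25%, 50% or 75% of the 51 were followed (assumed), the missing share of the ITT set would fall from 30% to 22.5%, 15% or 7.5%.

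**Power.** With 59.5 per arm, difference 1.07 and SD 1.83, power is 89.1% (normal approximation) or 88.5% (t-test), against 90% planned. Over a 10% to 40% loss it runs from 95.1% to 84.0%.

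**Bias.** Let p be the withdrawn share, taken as equal in both arms. Let Dc and Dw be the between-arm differences at Month 4 among completers and withdrawn subjects.

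- ITT difference = (1 − p) × Dc + p × Dw
- Overstatement by a completer analysis = p × (Dc − Dw)

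The documents give no value for Dw, so the gap Dc − Dw is an assumption:

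| Dc − Dw (NPRS units) | Overstatement at p = 0.30 |
|---|---|
| 0.5 | 0.15 |
| 1.0 | 0.30 |
| 2.0 | 0.60 |

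With Dc = 1.07 and Dw = 0, the ITT difference is 0.70 × 1.07 = 0.75, which is 0.32 below the completer value. At p = 0.10 it would be 0.90 × 1.07 = 0.96, and at p = 0.40 it would be 0.60 × 1.07 = 0.64.

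**What the planned methods assume.** After withdrawal for an adverse event or lack of response, Protocol 7.1 draws from baseline-like values, so the between-arm difference in those subjects is near zero. After other reasons it draws from same-arm subjects still in the study, so Dw is close to Dc. If all withdrawn subjects fell under one rule, the estimate would be near 0.75 or near 1.07. The recorded reason would then decide the result, with no post-withdrawal data to test it. In the SAP, the Level 3 table used for the primary endpoint reports change only for subjects with both values. Its own example has 18 at baseline, 16 at Month 4 and 16 in the difference.

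**If withdrawn subjects were followed.** Suppose all 170 are analysed with SD unchanged, and withdrawn subjects retain 0%, 25%, 50%, 75% or 100% of the effect (assumed). Power for the ITT difference is then 76.1%, 84.0%, 90.0%, 94.1% or 96.8%.

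**The case against.** The best defence is that the plan is less bare than the withdrawal sentence suggests. A reader might infer that these subjects contribute nothing. They do contribute: diary scores to withdrawal, an attempted exit assessment and adverse-event follow-up are all provided for. Protocol 7.1 also plans pattern-mixture sensitivity analyses and already applies a conservative rule to adverse-event and lack-of-response withdrawals. This stands, but it does not supply a Month 4 NPRS. The Month 4 procedure list in Protocol 4.8 has no separate clinic pain score, only a review of diary entries, so for the primary endpoint an exit visit adds little to the diary.

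A reader might also infer that stopping the device forces a subject out. The text does not say so. The grounds are permissive, sites contact subjects who under-use the device (Protocol 3.12.4 and 4.17), and a per-protocol set at 70% use or more implies that under-users remain in the ITT set. The supportable criticism is narrower: no off-device path is written down, and withdrawal ends outcome collection.

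Two further inferences fail. The documents do not show that missing outcomes come mainly from subjects with adverse events or no benefit; administrative decisions are also listed, and Protocol 6 reports no adverse events in an earlier study of this condition. Nor can all 51 be treated as recoverable, since subject request and loss to follow-up are among the grounds.

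**Conclusion.** The concern holds as a weakness in data collection that affects bias and the meaning of the ITT estimate. It is not a power problem. At the protocol's own 30% discontinuation, at most 51 of 170 subjects would lack a scheduled Month 4 NPRS, and an unknown part of these could have been followed. Each 1.0-unit shortfall in the between-arm difference among withdrawn subjects makes a completer estimate overstate the ITT difference by 0.30. No effect among them gives 0.75 against 1.07. These sizes assume equal withdrawal in both arms and are illustrations, not predictions. The gap is widened because Protocol 7.1 and SAP 7.2 contradict each other on whether missing values are imputed. It should be corrected, because uncollected outcomes cannot be recovered at analysis.

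**What to change.** The change concerns data collection only and leaves the grounds for stopping the device as they are.

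1. In Protocol 5 and SAP 4.4, distinguish stopping the device from withdrawing consent to data collection.
2. Unless consent is withdrawn, continue the morning ePRO NPRS through Day 120, with a diary instruction not tied to a treatment session, and hold the Month 4 visit on schedule.
3. Use these data in the ITT primary analysis. State how scores after stopping the device, or after a change in analgesics, are treated, and whether off-device subjects count as having completed Part A.
4. Reconcile SAP 7.2 with Protocol 7.1 for values that remain missing. Reconcile the withdrawal sentence with the adverse-event follow-up in Protocol 11.1.

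The cost is protocol and SAP wording, small diary and possibly consent changes, and site reminders. The diary already runs in any web browser. The estimate may be less favourable. If withdrawn subjects keep less than about half the effect, power for the ITT difference falls below 90%, to 76.1% if they keep none.

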- If the patient discontinues due to an AE lack of response, then missing data will be assumed to follow a distribution similar to the baseline values observed in the patient's randomized treatment.
- If the patient discontinues due to reasons other than AE or treatment response, at each time point, missing data will be assumed to follow a distribution similar to scores for patients that are still in the study and randomized to the same treatment group.

Results of the 120-day results, and the MMRM using the multiply imputed data, will be summarized using the SAS MIANALYZE procedure.

A hierarchical approach will be undertaken for the pre-specified secondary outcomes. Testing will occur in the listed sequence following testing of the primary endpoint.

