8. SUBJECT ACCOUNTING AND STUDY DISPOSITION

A complete accounting of subject participation in the study will be presented in Table 14.1.1 entitled *Subject Accounting and Final Study Disposition*. The Level 1 table layout will be used to present these results. The purpose of this table is to provide an accounting of subjects from their entrance into the study through the final visit and to account for subject evaluation in major analyses of safety and efficacy, including reasons for early study termination. The table will display the number and percentage of subjects who:

- were consented
- were screened
- were run-in failures
- are included in the ITT Population
- are included in the *Per protocol Population*
- completed the study

In addition, the reason for early study termination will be summarized separately using the number and percentage of subjects within each table column for each reason.

Listing 16.2.1 entitled *Subject Disposition* supports Table 14.1.1. This listing will be sorted by subject number and will contain the reason for discontinuation (if applicable), along with the date and last study visit attended.

Listing 16.2.2.1 entitled *Inclusion Criteria* displays the data from the Inclusion Criteria case report form (CRF). The data will be displayed for each subject and for each inclusion criterion. The listing will be sorted by subject number.

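### The protocol's imputation rule depends on knowing who left for lack of response, but the listed withdrawal reasons do not capture it and are not mapped to the rule's two branches

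*Protocol*

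**What the plan says.** Protocol 7.1, in its missing-data text, treats early discontinuation by cause. The first branch reads "If the patient discontinues due to an AE lack of response, then missing data will be assumed to follow a distribution similar to the baseline" and goes on to refer to the baseline values of the subject's own randomised group. The second begins "If the patient discontinues due to reasons other than AE or treatment response, at each time point" and draws on the scores of subjects in the same arm who have not left.

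Protocol 5 gives six circumstances in which a subject may be withdrawn: a plain subject request, noncompliance, an adverse event (decided by investigator or subject), an investigator or sponsor decision, "Request for withdrawal by the subject for reasons other than an intolerable AE", and loss to follow-up. SAP 4.4 repeats the same six. None is lack of response or inadequate pain relief. Protocol 5 also ends data collection once a subject is withdrawn, apart from an effort to complete the Month 4 assessments beforehand.

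SAP 8 says that "the reason for early study termination will be summarized separately" but names no categories. The table conventions in SAP 7 have zeros shown for termination reasons that nobody met, which implies a predefined list. SAP 7.2 says that missing values will not be imputed and provides an analysis of the last recorded observation.

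**The concern.** The two branches make opposite assumptions. One returns the subject to the baseline level, so the benefit is lost. The other gives the subject the experience of those who stayed on the same device. Which one applies turns on the recorded reason, and the only list of reasons in either document lacks one of the two that trigger the first branch. A subject who stops because the device does not help fits most naturally under the plain request item. On the wording of the second branch, that leads to same-arm imputation.

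The request items also overlap with each other and with the adverse-event item. A subject who asks to leave because of a tolerable adverse event could be recorded as an adverse event (baseline-like) or as a request (same-arm).

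At stake is whether the cautious part of the rule operates as intended, and whether the imputed result on the primary endpoint is fixed by the plan or by how each site words an exit. Because follow-up data stop at withdrawal, a reason not recorded at exit may be impossible to recover.

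**Working it through.** **Inputs from Protocol 7.4.** The mean improvement and SD on PEMF come from "from baseline to 60 days was 1.79 ± 1.83 units". The contrast comes from "Assuming a placebo effect of 40% results in an assumed between group difference of 1.07 units": sham improvement 0.40 × 1.79 = 0.716, difference 1.79 − 0.716 = 1.074. There are 85 subjects per arm and 30% discontinuation for all reasons.

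**The plan's own figure.** The protocol states "Based on alpha = 0.05 and 90% power, a sample size of 62 patients per treatment group would be needed", using a "two-sided sample t-test for the NPRS". With the normal approximation, n = 2 × [1.83 × (1.960 + 1.282) / 1.07]² = 61.5, so 62 per group. The t-based calculation gives 62.4 with a difference of 1.07 and 62.0 with 1.074. The figure reproduces, so these means are a fair basis for the check.

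**Assumptions.**
- The documents do not split discontinuation by reason. Let fA and fS be the shares of the active and sham arms that leave for lack of response. I use 5% to 30%, the top being the all-reason rate.
- Baseline-like imputation gives these subjects a mean change of 0.
- Same-arm imputation gives them the full arm mean, and all of them take that route.
- The 60-day open-label means stand in for Month 4.

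**Formulas.**
- Same-arm branch: difference = 1.79 − 0.716 = 1.074, whatever the shares.
- Baseline branch: difference = 1.79 × (1 − fA) − 0.716 × (1 − fS).
- Same-arm minus baseline: 1.79 × fA − 0.716 × fS.
- Nominal power at 85 per arm: Φ(difference / [1.83 × √(2/85)] − 1.96), holding the SD at 1.83 and treating imputed scores as if observed.

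**Results.**

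| Active share | Sham share | Difference, baseline branch | Same-arm minus baseline | Nominal power, baseline branch |
|---|---|---|---|---|
| 0% | 0% | 1.074 | 0 | 0.969 |
| 5% | 5% | 1.020 | 0.054 | 0.953 |
| 10% | 10% | 0.967 | 0.107 | 0.931 |
| 15% | 15% | 0.913 | 0.161 | 0.902 |
| 20% | 20% | 0.859 | 0.215 | 0.865 |
| 30% | 30% | 0.752 | 0.322 | 0.764 |
| 15% | 5% | 0.841 | 0.233 | 0.850 |
| 5% | 15% | 1.092 | −0.018 | 0.973 |

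**Where the direction turns.** The shift is zero when 1.79 × fA = 0.716 × fS, that is, when fS / fA = 1.79 / 0.716 = 2.5. For example, 5% active and 12.5% sham give 0.0895 on both sides. Above that ratio, same-arm imputation understates the contrast relative to the baseline rule.

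**The case against.** The strongest reply is that the six items are circumstances in which a subject may be withdrawn, not declared form codes. The termination form is not in the documents, and SAP 8 could tabulate reasons that the form captures separately. The imputation rule names the cause itself, so on a literal reading a subject who asks to leave because the device does not help belongs in the baseline-like branch. This stands. A reader might infer that such a subject can only be recorded as a request, or that the baseline-like branch can never be triggered for lack of response. The documents do not support that. They show only that nothing ensures capture. The zero-filled termination table suggests a predefined list, and the six items are the only candidate in view.

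Second, SAP 7.2 imputes no values, and Protocol 7 leaves analysis detail to the SAP. Under the SAP as written there is no reason-based result to distort. This also stands: the problem arises only if the protocol rule is applied, and the conflict has to be settled first.

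Third, a reader might infer that same-arm imputation always favours the device. It raises each arm's own mean improvement, but the contrast can move either way, as the last row of the table shows.

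Fourth, a reader might infer that a subject who changes analgesics for uncontrolled pain would be withdrawn and recorded as noncompliant. Protocol 4.19 disallows such changes, but no passage says that they lead to withdrawal or how they would be recorded.

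Fifth, Protocol 7.1 also plans sensitivity analyses for different missing-data patterns, a repeated-measures model on observed data, and an analysis to the last non-missing weekly mean. The last two do not use the reason for leaving. They soften the consequence but do not make the reason-based rule executable.

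**Conclusion.** The gap is real, of modest size, and cheap to close. The reason-based rule needs an input that the listed reasons do not provide, and no text assigns those reasons to branches. Subjects who leave for lack of response are therefore likely, though not certain, to be imputed as same-arm. If the protocol rule is used, the result depends on site coding.

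On the plan's means and assumed equal shares of 5% to 30%, the difference is 1.02 to 0.75 under the baseline rule against 1.07 under same-arm. For any given shares this is roughly an upper bound on the shift. If the imputation conditions on a subject's earlier scores, which Protocol 7.1 does not specify, a poor course before exit carries forward and the gap narrows. It also narrows if some sites do record the cause. No net direction can be claimed, because it depends on whether the sham share exceeds about 2.5 times the active share. Confidence is moderate, chiefly because the termination form is not available.

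**What to change.** 1. Reconcile Protocol 7.1 with SAP 7.2, so that both state whether missing scores are imputed and by which rule.
2. Add lack of response or insufficient pain relief as a recorded discontinuation reason. Make the request categories mutually exclusive, and require one primary reason per subject, recorded before unblinding.
3. Correct the wording of the first branch, where adverse event and lack of response run together without a conjunction, and use matching terms in the second. State in Protocol 7.1 and the SAP which recorded reasons go to each branch.

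These changes concern what is recorded and how it is analysed. They do not alter when a subject may be withdrawn.

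The cost is one extra category on the form and a few sentences in each document. The imputed effect may change slightly, in either direction.
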